8.1.5 Subject Stopping Guidelines

This guideline is to be used to indicate boundaries requiring discussion by the Data and Safety Monitoring Board (DSMB) and is designed to assist the independent DSMB in overseeing the study. The DSMB may also request additional interim analyses and develop other criteria including provision for monitoring of potential late effects to determine when to intervene in the enrollment or treatment of subjects in the study. The first more conservative stopping guideline is to monitor subjects for unexpected SAEs where there is a reasonable possibility that the study product or administration procedure caused the event within 30 days of administration including subject death, grade 3 myocardial infarction, grade 3 hemodynamically unstable ventricular tachycardia or grade 3 LV perforation. Study accrual and further treatment of subjects will be put on hold if any subjects experience one of these events. The DSMB will be notified within 24 hours of the occurrence of these events and will be convened within 3 business days to review the event and study.

The following are subject stopping guidelines:

5. Any subject who develops persistent (that is, still existing more than 3 hours after the end of IP infusion) cardiorespiratory signs or symptoms (for example, shortness of breath, tachypnea, tachycardia, Bradycardia, hypotension, or palpitations) will continue with all scheduled follow-up if such follow-up is considered safe in the opinion of the Investigator.
6. Any subject whose infusion is stopped due to cardiorespiratory distress will receive no further IP infusions but will continue with all scheduled follow-up if such follow-up is considered safe in the opinion of the Investigator.
7. Any subject who develops any sign or symptom that, at the discretion of the Investigator, warrants the discontinuation of infusion will receive no further IP infusions but will continue with all scheduled follow-up if such follow-up is considered safe in the opinion of the Investigator.
8. Infusion of the IP may be stopped if there is an adverse event that the Investigator believes is related to the IP or if there is an issue with the IP infusion.

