9. The proportion of subjects experiencing TE-SAE as defined in Section 2.2.1 will be monitored within 30 days of infusion. This guideline is designed to assist the independent DSMB in overseeing the study and indicate boundaries needing discussion by the DSMB. The DSMB may also request additional interim analyses

and develop other criteria including provision for monitoring of potential late effects to determine when to intervene in the enrollment or treatment of subjects in the study.

10. Monitoring of key safety endpoints (refer to Table 8 in section 2.2.1) will be conducted.
11. The stopping guidelines serve as a mechanism for consultation with the DSMB for additional review, and are not formal “stopping rules” that would mandate automatic closure of study enrollment. It is designed to assist the independent DSMB in overseeing the study. The DSMB may also request additional interim analyses and develop other criteria including provision for monitoring of potential late effects to determine when to intervene in the enrollment or treatment of subjects in the study.
12. Study accrual and further treatment of subjects will be stopped if multiple (i.e. more than 1) subjects develop cardiorespiratory signs and symptoms that are persistent or lead to discontinuation of infusion.

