9.3 Interim Analyses

Interim analyses will be conducted at times coincident with regularly scheduled meetings of the Data and Safety Monitoring Board (DSMB) at approximately six-month intervals. The DSMB Chair will be notified each time an SAE occurs. After all subjects in phase I have been followed for 30 days, at that time an independent DSMB will review all available data to make an independent recommendation to either keep the specified randomized dose 1:1:1 or to recommend a dose modification for the randomized placebo study.

Policies of the DSMB will be described in the DSMB Charter, which will be prepared by the DSMB prior to study initiation. The stopping guidelines serve as a trigger for consultation with the DSMB for additional review, and are not formal “stopping rules” that would mandate automatic closure of study enrollment.

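### Section 8.1.5 item 12 orders accrual and treatment stopped after a second qualifying subject, while item 11, the section's preamble and Section 9.3 say the guidelines only prompt DSMB consultation

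*Combined protocol and SAP*

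**What the plan says.** Item 12 of Section 8.1.5 states: "Study accrual and further treatment of subjects will be stopped if multiple (i.e. more than 1) subjects develop cardiorespiratory signs". The signs that count are limited to "cardiorespiratory signs and symptoms that are persistent or lead to discontinuation of infusion". Item 5 of the same list explains persistence as "still existing more than 3 hours after the end of IP infusion" and gives examples: "shortness of breath, tachypnea, tachycardia, Bradycardia, hypotension, or palpitations".

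Item 11, directly above, says: "The stopping guidelines serve as a mechanism for consultation with the DSMB for additional review". It adds that they are not formal rules "that would mandate automatic closure of study enrollment". Section 9.3 repeats the point, again denying that the guidelines are rules that "would mandate automatic closure of study enrollment". The preamble of 8.1.5 likewise presents the guideline as marking limits for the DSMB to discuss.

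The preamble also sets out a first guideline, for certain unexpected and possibly related serious events within 30 days. There the instruction is: "Study accrual and further treatment of subjects will be put on hold if any subjects experience one of these events". It comes with a process: the DSMB is told within 24 hours and meets within 3 business days.

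**The concern.** Item 12 is worded as an order and the text around it as advice, and both apply to the same occurrence. The protocol does not say which prevails.

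This rule decides whether enrollment and dosing continue in a 42-subject trial. If the second qualifying subject appears midway through the randomized phase, staff who follow item 12 literally would stop the study. Staff who follow item 11 could keep treating while the DSMB is consulted. The first course could end the comparison of umbilical cord cells, bone marrow cells and placebo without anyone having decided to end it. The second could breach a written safety commitment. Either could later be recorded as a protocol deviation.

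**Working it through.** **1. The two guidelines side by side**

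| Feature | First guideline (8.1.5 preamble) | Item 12 |
|---|---|---|
| Trigger | Any one subject with a listed event | More than 1 subject with a qualifying sign |
| Instruction | Hold | Stop |
| DSMB notification | Within 24 hours | Not stated |
| DSMB meeting | Within 3 business days | Not stated |
| Restart path or decision-maker | Follows from the DSMB review | Not stated |
| Count across pilot and randomized phases | Not needed, one event suffices | Not stated |

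**2. What each reading implies for the same two subjects**

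- Termination: item 12 taken literally, since it uses a different verb from the first guideline and names no review.
- Pause: item 12 taken as a halt, with the DSMB advising. This is plausible, but the review step has to be supplied by the reader.
- Consultation only: item 11 and Section 9.3 taken as governing every guideline, so accrual need not stop.

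Appendix 1 does not settle it. Its list of stopping guidelines covers the individual-subject rules and has no counterpart to item 12.

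**3. Chance of reaching the trigger (supporting information only)**

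The documents give no operating characteristic for item 12, so there is no figure to reproduce. They also give no background rate for the qualifying event. The rates below are assumptions.

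Inputs: a trigger of 2 or more subjects (item 12); n = 42 infused subjects (synopsis), being 12 pilot and 30 randomized (Section 3.1); p = assumed chance per subject of a qualifying sign from any cause.

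Formula: P(X ≥ 2) = 1 − (1 − p)^n − n·p·(1 − p)^(n − 1)

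Example, n = 42, p = 0.02: 1 − 0.98^42 − 42 × 0.02 × 0.98^41 = 1 − 0.4281 − 0.3669 = 0.205.

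| Assumed rate p | n = 42, one count over both phases | n = 30, randomized phase alone |
|---|---|---|
| 1% | 6.6% | 3.6% |
| 2% | 20.5% | 12.1% |
| 5% | 62.8% | 44.6% |
| 10% | 93.2% | 81.6% |

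Solving P(X ≥ 2) = 0.5 gives p of about 4.0% for n = 42 and 5.5% for n = 30. The two columns also show that whether the count carries over changes the answer: at 5%, 62.8% against 44.6%.

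**The case against.** The strongest reply is that the section should be read as a whole. The preamble and item 11 describe the stopping guidelines in general, item 12 sits immediately below, and Section 9.3 repeats the description. Sections 9.4.3.3 and 9.4.5.2 make termination a DSMB recommendation that the investigator then reviews. On that reading item 12 halts accrual, the DSMB advises, and nothing ends automatically. This may well be what was meant, and it weighs against assuming that item 12 is a termination rule. It does not remove the gap. Item 12 refers to no review, and the first guideline shows that the authors wrote out a hold and a review where they wanted them.

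A reader might also infer from the table that the rule would often be reached by chance and that the trial would probably end early. The documents do not support that. It needs a background rate of about 4% for an even chance over 42 subjects, and no such rate is given; at 1% the chance is 6.6%. The nearest text suggests a low rate: Section 6.4 reports no infusion-related toxicity in prior trials, and Section 8.14 reports no adverse events attributed to administration. Those statements concern toxicity or attributed events, whereas item 12 requires no attribution, so they do not fix the rate either. Nor would any two cardiorespiratory events suffice: the signs must outlast 3 hours or cause the infusion to be discontinued.

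Finally, a reader might object to the low count, the ungraded signs or the inclusion of placebo subjects, or ask for counts by arm. The first three are conservative choices open to the clinical team and the DSMB. The last is largely provided already: under Section 9.4.3.3 the closed-session report gives enrollment and adverse events by treatment group.

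**Conclusion.** The contradiction stands and depends on no assumed rate. Item 12 conflicts with item 11, the 8.1.5 preamble and Section 9.3, and it lacks the notification, review and restart steps of the first guideline. As written, one occurrence permits three different actions.

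The probabilities only illustrate why the status of the rule matters. They assume independent subjects, a constant rate and all planned subjects infused; the n = 42 column further assumes a single count over both phases, which item 12 does not specify. They do not show that the threshold is wrong, and this point takes no position on which stopping rule is clinically right.

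**What to change.** Reconcile item 12 with item 11, the 8.1.5 preamble and Section 9.3, and state three things:

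- whether reaching the trigger is a pause pending DSMB review or a termination, and if a pause, when the DSMB is told, when it meets and how treatment may resume;
- who takes the decision;
- whether the count runs across the pilot and randomized phases or starts afresh.

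The clinical team and the DSMB choose the content of the rule. As supporting information for them, add a short table giving the chance of reaching whatever trigger they adopt under a stated range of assumed background rates, labelled as assumptions.

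The cost is a few sentences of protocol wording and one small table, with no added subjects, visits or procedures.

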8.1.6 Subject observation and discontinuation after IP administration

The IP administration guidelines in **Appendix 1** list the study requirements for subject observation and discharge after IP administration.

8.2 Definition of an Adverse Event

An Adverse Event (AE) is any untoward medical occurrence in a subject or clinical investigation subject temporally associated with the use of a medicinal product, whether or not considered related to the medicinal product. The occurrence does not necessarily have to have a causal relationship to the treatment received in the study. An AE can therefore be any unfavorable and unintended sign (including an abnormal laboratory finding, for example), symptom, or disease (new or exacerbated) temporally associated with the use of a medicinal product, whether or not considered related to the medicinal product.

Examples of an AE include:

- Exacerbation of a chronic or intermittent pre-existing condition including either an increase in frequency or intensity of the condition.
- Significant or unexpected worsening or exacerbation of the condition/indication under study.
- A new condition detected or diagnosed after study therapy administration even though it may have been present prior to the start of the study.

- Pre- or post-treatment events that occur as a result of protocol-mandated procedures (e.g., invasive protocol-defined procedures, modification of a subject's previous treatment regimen).

An AE does **not** include:

- Medical or surgical procedures (e.g., colonoscopy, biopsy). The medical condition that leads to the procedure is an AE.
- Social or convenience hospital admissions where an untoward medical occurrence did not occur.
- Day to day fluctuations of pre-existing disease or conditions present or detected at the start of the study that do not worsen.
- The disease/disorder being studied or expected progression, signs, or symptoms of the disease/disorder being studied unless more severe than expected for the subject's condition.

8.3 Definition of Adverse Reaction

An adverse reaction is any adverse event caused by a drug. Adverse reactions are a subset of all suspected adverse reactions for which there is reason to conclude that the drug caused the event.

8.4 Definition of Suspected Adverse Reaction

Suspected adverse reaction means any adverse event for which there is a reasonable possibility that the drug caused the adverse event. For the purposes of IND safety reporting, 'reasonable possibility' means there is evidence to suggest a causal relationship between the drug and the adverse event. A suspected adverse reaction implies a lesser degree of certainty about causality than adverse reaction, which means any adverse event caused by a drug.

8.5 Definition of Serious

An adverse event (AE) or suspected adverse reaction is considered "serious" if it:

1. results in death
2. is life-threatening (at risk of death at the time of the event)
3. requires in inpatient hospitalization or prolongation of existing hospitalization

NOTE: Complications that occur during hospitalization are AEs. If a complication prolongs hospitalization or fulfills any other serious criteria, the event is serious.

Hospitalization for elective treatment of a pre-existing condition that did not worsen from baseline is not considered to be an AE.

4. results in disability/incapacity

*NOTE: The term **disability** means a substantial disruption of a person's ability to conduct normal life functions. This definition is not intended to include experiences of relatively minor medical significance such as uncomplicated headache, nausea, vomiting, diarrhea, influenza, accidental trauma (i.e., sprained ankle) that may interfere or prevent everyday life functions but do not constitute a substantial disruption.*

5. is a congenital anomaly/birth defect.

Important medical events that may not result in death, be life-threatening, or require hospitalization may be considered an SAE when, based upon appropriate medical judgment, they may jeopardize the subject and may require medical or surgical intervention to prevent one of the outcomes listed in the above definition.

8.6 Definition of Unexpected

An adverse event or suspected adverse reaction is considered “unexpected” if it is not listed in the investigator brochure or is not listed at the specificity or severity that has been observed; or, if an investigator brochure is not required or available, is not consistent with the risk information described in the general investigational plan or elsewhere in the current application.

8.7 Clinical Laboratory Assessments and Other Abnormal Assessments as Adverse Events and Serious Adverse Events

Abnormal laboratory findings (e.g. clinical chemistry, hematology) or other abnormal assessments (e.g., vital signs) that are judged by the Investigator as clinically significant will be recorded as AEs or SAEs if they meet the definition of an AE as defined in Section 8.3 (“Definition of an Adverse Event”) or SAE, as defined in Section 8.6 (“Definition of a Serious Adverse Event”). Clinically significant abnormal laboratory findings or other abnormal assessments that are detected during the study or are present at screening and significantly worsen following the start of the study will be reported as AEs or SAEs. However, clinically significant abnormal laboratory findings or other abnormal assessments that are associated with the disease being studied, unless judged by the Investigator as more severe than expected for the subject's condition, or that are present or detected at the start of the study but do not worsen, will not be reported as AEs or SAEs.

The Investigator will exercise medical judgment in deciding whether abnormal laboratory values are clinically significant.

8.8 Recording of Adverse Events and Serious Adverse Events

The Investigator should review all documentation (e.g., hospital progress notes, laboratory, or diagnostic reports) relative to the event being reported. The Investigator will then record all relevant information regarding an AE/SAE into the electronic data system. It is not acceptable for the Investigator to send photocopies of the subjects' medical records in lieu of completion of the appropriate AE/SAE pages.

The Investigator will attempt to establish a diagnosis of the event based on signs, symptoms, and/or other clinical information. In such cases, the diagnosis should be documented as the AE/SAE and not the individual signs and symptoms.

SAEs will be reported to the IRB within 10 working days or within 24 hours if the event is life-threatening or results in death.

Pregnancies

Subject pregnancy must be reported to the Principal Investigator within 1 working day of knowledge of the event. Any subject that becomes pregnant during the study must be promptly withdrawn from the study. Follow-up information regarding the outcome of the pregnancy and any postnatal sequelae in the infant will be required.

8.9 Intensity of Adverse Events and Serious Adverse Events

The Investigator will make an assessment of intensity for each AE and SAE reported during the study. The assessment will be based on the Investigator's clinical judgment. The intensity of each AE and SAE should be assigned to one of the following categories:

Mild:	An event that is easily tolerated by the subject, causing minimal discomfort and not interfering with everyday activities.
Moderate:	An event that is sufficiently discomforting to interfere with normal everyday activities.
Severe:	An event that prevents normal everyday activities.
Life-threatening:	Immediate risk of death.

An AE that is assessed as severe should not be confused with an SAE. Severity is a category utilized for rating the intensity of an event; and both AEs and SAEs can be assessed as severe. An event is described as 'serious' when it meets one of the pre-defined outcomes as described in Section 8.6, "Definition of Serious."

8.10 Causality of Adverse Events and Serious Adverse Events

The Investigator is obligated to assess the causality between study therapy and the occurrence of each AE/SAE. The Investigator will use clinical judgment to determine if there is a reasonable possibility that the biological action of the study therapy was responsible for AE/SAE being reported. Alternative causes such as natural history of the underlying diseases, concomitant therapy, other risk factors, and the temporal relationship

of the event to the study therapy will be considered and investigated. The Investigator will also consult the Clinical Investigator's Brochure and/or Product Information, for marketed products, in the determination of his/her assessment.

The Investigator will use the following questions when assessing causality of an adverse event to study therapy.

Is there a reasonable possibility that the study therapy caused the event? Reasonable possibility implies that there is evidence that the event was caused by the study product. An affirmative answer designates the event as a suspected adverse reaction.

There may be situations when an SAE has occurred and the Investigator has minimal information to include in the initial report. However, it is very important that the Investigator always make an assessment of causality.

The relationship between AEs and the study exposure will be classified by the investigator as:

- None: No relationship. Related to other known etiologies, conditions, or exposures.
- Unlikely: Current knowledge suggests that a relationship is unlikely.
- Possible: A plausible temporal sequence or response pattern exists but the AE may be related to other known etiologies, conditions, or exposures.
- Probable: A plausible temporal sequence or response pattern exists and the AE cannot be related to other known etiologies, conditions, or exposures.
- Definite: A plausible temporal sequence or response pattern exists and the AE can be confirmed by re-challenge or with other supporting data.

8.11 Follow-Up of Adverse Events and Serious Adverse Events

After the initial AE/SAE report, the Investigator is required to proactively follow each subject and provide further information on the subject's condition. All AEs and SAEs documented at a previous visit/contact that are designated as ongoing will be reviewed at subsequent visits/contacts.

Adverse events and SAEs will be followed until resolution, until no further changes in the event are expected (i.e. the point at which a subject experiencing a critical adverse event is treated successfully and stabilized even though they may continue to experience lingering sequelae that may never resolve), until the subject is lost to follow-up, or until it is agreed that further follow-up of the event is not warranted (e.g. non-serious, study therapy unrelated, mild or moderate adverse events ongoing at a subject's final study visit). If a subject dies during participation in the study or during a recognized follow-up period, the Investigator will provide a copy of any post-mortem findings, including histopathology.

New or updated information will be recorded by modifying the AE forms in the electronic data system

8.12 Timeframes for Submitting SAE Reports

Once an Investigator becomes aware that an SAE has occurred in a study subject, he/she will record the information in the electronic data record within 48 hours. Any fatal or life-threatening event must be reported within 24 hours. If the Investigator does not have all information regarding an SAE, he/she will not wait to receive additional information before recording the event in the data system and completing as much information known at the time of the submission. The reporting timeframes for any SAE occurring during the study are summarized in Table 12.

TABLE 12
Serious Adverse Event Reporting Requirements

	Initial Reports		Follow-Up Reports
Type of SAE	Fatal or Life-Threatening	Other SAEs	Any SAE
Reporting Timeframes	24 hours	48 hours	48 hours
Documents Required	24 hours: Complete as much information in the electronic data system that is known. 48 hours: Fully complete all AE forms	Fully completed AE forms	Updated AE Forms

